1.0 Objectives

Primary Objective:

To evaluate the efficacy of Ferric Carboxymaltose (Injectafer) in anemia in gastrointestinal stromal tumor (GIST) patients planned to receive or receiving systemic therapy and presenting with anemia.

Secondary Objectives:

- (1) To evaluate the toxicity of Ferric Carboxymaltose in GIST patients planned to receive or receiving systemic therapy and presenting with anemia.
- (2) To evaluate effect of Ferric Carboxymaltose on patient reported outcomes (fatigue) by Functional Assessment of Cancer Therapy-Fatigue Scale (FACT-F).

2.0 Background

2.1 Cancer and Chemotherapy-related Anemia

Anemia is a common complication in patients who have cancer and those who receive Chemotherapy [1]. Depending on the type of cancer, 30% to 90% of patients have anemia, defined as a hemoglobin <11.0 g/dL [2, 3]. Results from a survey, including more than 15,000 cancer patients, demonstrated that the incidence of anemia was 53.7%; however, only 38.9% of the patients with anemia were treated. In relation to the patient, anemia is a burden as it may affect one's quality of life, contributing to symptoms such as fatigue and weakness [4, 5]. Anemia in cancer patients is often multifactorial and can be caused by hemolysis, iron deficiency due to blood loss, inadequate nutrition, impaired RBC production due to direct effects of the cancer or myelosuppressive chemotherapy or radiation therapy [5]. The severity of anemia depends on the type and extent of the cancer, the schedule and intensity of therapy, and whether the patient has received prior chemotherapy and/or radiation.

Iron deficiency anemia (IDA), is the top-ranked type of anemia worldwide [6]. The reported prevalence of IDA in cancer is around 32-60%. Iron deficiency (ID) plays a pivotal role in the development of anemia in cancer. ID in cancer may be separated into two components, absolute iron deficiency and functional iron deficiency. Absolute ID is defined as depleted iron stores. Most iron-deficient patients with cancer present with functional ID [7]. Functional ID is characterized by iron sequestration, and thus, the lack of available iron with normal or elevated ferritin levels. Functional ID is often caused by a chronic inflammatory state which many cancer patients may have [8]. Two studies have examined the administration of IV iron without ESAs, and both studies demonstrated that IV iron alone can reduce transfusion rates [9, 10].

2.2 Anemia in GIST Patients Receiving Systemic Therapy

A gastrointestinal stromal tumor (GIST) is a type of tumor that occurs in the gastrointestinal tract, most commonly in the stomach or small intestine [11]. Chronic

blood loss is more common for GIST patients [12]. Many GIST patients are diagnosed with anemia due to chronic blood loss [13]. GIST patients presenting anemia can be due to iron deficiency anemia either from inadequate iron intake or from blood loss (as from a GIST bleeding into the GI tract), surgery, or drug-induced anemia; Gleevec and other Tyrosine Kinase Inhibitors (TKIs) may decrease production of new red blood cells [14].

2.3 Prevention/Treatment for IDA

Iron replacement therapy is essential for replenishing iron stores and raising hemoglobin levels in patients with IDA, regardless of the etiology, and can be administered orally, intramuscularly, or intravenously [6,15]. Patients with IDA should receive iron supplementation and the prescribed use of oral iron is a convenient, inexpensive, and effective treatment regimen in stable patients. However, use of oral iron is limited by side effects, including nausea, vomiting, constipation, and metallic taste, resulting in non-adherence and limited treatment response [6, 15].

There is considerable efficacy and safety experience with the various oral iron preparations available. Intravenous iron replacement therapy is also a treatment alternative. However, prior to the approval of non-dextran formulations, the risk of systemic adverse reactions restricted their use [6, 15].

More recently approved, non-dextran intravenous irons, like iron sucrose and iron gluconate, do not contain the dextran moiety, but they have significant dosage and administration rate limitations [16, 17]. If the body's ability to handle (i.e., sequester, store, and transport) iron is overwhelmed, a reaction to excess free iron referred to as a bioactive iron reaction may occur. These IV iron compounds carry a significant risk of bioactive iron reactions at higher doses. These reactions are characterized by hypotension (without allergic signs) accompanied by pain in the chest, abdomen, flank and/or nausea, vomiting, diarrhea [6, 15].

2.4 Injectafer, a Newly Approved Iron Preparation

Injectafer (Ferric Carboxymaltose Injection) is a stable Type I polynuclear iron (III)-hydroxide carbohydrate complex developed as an intravenous iron replacement therapy for the treatment of IDA. After intravenous administration, Injectafer is mainly found in the liver, spleen, and bone marrow. The iron slowly dissociates from the complex and can be efficiently used in the bone marrow for hemoglobin synthesis. The carbohydrate moiety of Injectafer is metabolized by the glycolytic pathway [18-21].

Due to its structure, Injectafer is more stable than iron gluconate and iron sucrose, producing a slow delivery of the complexed iron to endogenous iron binding sites and has an acute toxicity in animals approximately 1/5 that of iron sucrose. These characteristics of Injectafer make it possible to administer much higher single doses over shorter periods of time than iron gluconate or iron sucrose, resulting in the need for fewer administrations to replenish iron stores, consequently making it better suited for outpatient use (Table below).

Comparison of the Administration of Intravenous Iron with Currently US Available Iron Preparations

Iron Preparation	Test Dose Required	Maximum Infusion Dose	Infusion Time	Number of Infusions
Iron dextran	Yes	100 mg*	2 minutes	15 + test dose
Iron gluconate	No	125 mg	10 minutes	12
Iron sucrose	No	200 mg	5 minutes	8
Iron sucrose	No	400 mg	2.5 hours	4
Ferumoxytol	No	510 mg	< 1 minute	3
Injectafer	No	750 to 1000 mg**	8 to 15 minutes	2

* Higher doses are administered off label and are approved outside the US

**1000 mg maximum dose is approved in the European Union; 750 mg maximum is the U.S. FDA approved dose that will be evaluated in this trial

Compared to other available intravenous iron preparations, the larger Injectafer doses result in less frequent administration of intravenous iron and represents an improvement in convenience for patients and physicians, especially for those individuals with conditions amenable to complete replacement dosing in a single setting such as heavy uterine bleeding, inflammatory bowel disease, bariatric surgery, hereditary hemorrhagic telangiectasia or any condition where blood loss exceeds maximum absorption [18-21].

2.4.1 Pharmacodynamics

A clinical pharmacokinetic study (VIT-IV-CL-001) using positron emission tomography (PET) demonstrated a fast initial elimination of radioactively labeled iron (Fe) $^{52}\text{Fe}/^{59}\text{Fe}$ Injectafer from the blood, with rapid transfer to the bone marrow and rapid deposition in the liver and spleen. Eight hours after administration, 5 to 20% of the injected amount was still in the blood, compared with 2 to 13% for iron sucrose. The projected terminal half-life ($t_{1/2}$) was calculated to be approximately 16 hours, compared to 3 to 4 days for iron dextran and 6 hours for iron sucrose. An ascending dose pharmacokinetic study (VIT-IV-CL-002), demonstrated that following the 500 and 1,000 mg Injectafer dose, the majority of the Injectafer iron complex was utilized or excreted by 72 hours [18-21].

Using PET it was demonstrated that red cell uptake of ^{59}Fe and ^{52}Fe from Injectafer ranged from 61% to 99%. In patients with iron deficiency, red cell uptake of radio-labeled iron ranged from 91% to 99% at 24 days after Injectafer dose. In patients with renal anemia, red cell uptake of radio-labeled iron ranged from 61% to 84% after 24 days Injectafer dose.

After administration of a single dose of Injectafer of 100 to 1000 mg of iron in iron deficient patients, maximum iron levels of 37 $\mu\text{g}/\text{mL}$ to 333 $\mu\text{g}/\text{mL}$ were obtained respectively after 15 minutes to 1.2 hours post dose. The volume of distribution was estimated to be 3 L. The iron injected or infused was rapidly cleared from the plasma, the terminal half-life ranged from 7 to 12 hours. Renal elimination of iron was negligible [18-21].

2.4.2 Clinical Experience

The efficacy of Injectafer® for the treatment of IDA was demonstrated in 2 randomized, open-label, controlled clinical studies (1VIT09030 and 1 VIT09031). In these 2 studies, Injectafer® was administered at a dose of 15 mg/kg body weight up to a maximum single dose of 750 mg of iron on 2 occasions separated by at least 7 days up to a cumulative dose of 1500 mg of iron [21-23].

Study 1 VIT09031 enrolled subjects with iron-deficiency anemia who had an unsatisfactory response to oral iron or who were intolerant to or inappropriate for oral iron therapy during the 14-day, oral iron run-in period. Study 1VIT09030 enrolled subjects with iron-deficiency anemia and impaired renal function [21-23].

The overall incidence of treatment-emergent serious adverse events in the 2 studies was 12.8% in the Injectafer® group and 12.5% in the pooled comparators group. No notable differences (1.0% and at least a 2-fold difference in incidence) were observed between the Injectafer® group and the pooled comparators groups for specific events.

The overall incidence of treatment-emergent adverse events resulting in premature discontinuation of study drug was 2.9% in the Injectafer® group and 2.1% in the pooled comparators group. The most common treatment-emergent adverse events resulting in premature discontinuation of study drug in the Injectafer® group were flushing and hypertension (0.5% and 0.6%, respectively) [21-23].

The percentage of subjects with treatment-emergent low phosphorus, defined as a baseline value that was Grade 0, 1, or 2 and decreased to a value defined as Grade 3 (<2.0 to 1.0 mg/dL) or Grade 4 (<1.0 mg/dL) per Common Terminology Criteria for Adverse Event version 3.0, was the only notable difference between the Injectafer® (29.6%) and the pooled comparators (0.7) groups. Mean decreases from baseline in phosphorus in the Injectafer® group were highest at Day 14 and were returning toward baseline at Day 28/35 in Studies 1VIT09030 and 1VIT09031. The trend toward baseline continued through Day 56 in Study 1VIT09030 [21-23].

Safety results for 5799 Injectafer®-treated subjects treated in 20 short-term Phase 2/3 studies of iron-deficiency anemia or congestive heart failure (CHF) were similar to studies 1VIT09030 and 1VIT09031 [21-23].

In summary, Injectafer® is a safe and effective treatment of IDA in adult patients who are [20]:

- Intolerance to oral iron or have had unsatisfactory response to oral iron;
- Non-dialysis-dependent chronic kidney disease.

2.5 Rationale for the Study

The incidence of anemia in patients with gastrointestinal stromal tumor (GIST) receiving TKIs therapy is high [13]. Anemia in GIST patients can be multifactorial such as: anemia of chronic disease, primary therapy, surgery, blood loss and Iron/vitamin deficiency [6].

In our experience, GIST patients with anemia and IDA do response to oral iron if they can tolerate it. In our observations in patients with GIST on iron therapy, approximately 29% of patients tolerated and had response to oral iron vs 75% had response to IV iron such as iron sucrose. This experience is similar to response rate (73%-77%) reported with iv iron in clinical trials in cancer patients receiving chemotherapy [27]. However, the GIST patients seem to have lower tolerance to oral iron due to the underlying disease and treatment with TKIs. This can explain lower success rate (~29%) in our experience as compared to ~45% reported in clinical trials to oral drugs in cancer patients receiving chemotherapy. Also, multiple infusions of iron sucrose are needed to deliver the total dose of iron. Patients with GIST often present with IDA and anemia often worsens during therapy with TKIs like Gleevec [14]. These patients often have nausea from their systemic therapy and not all patients tolerate oral iron well. Also there is a time lag for response to oral iron. Injectafer is a newly approved, non-dextran IV iron that can be administered in a large dose of 2 infusions 1 week apart (15 mg/kg for a maximum single dose of 750 mg, a total of up to 1500 mg). The safety profile is excellent and has been found effective in correcting IDA. Based on these observations, we are proposing a clinical trial of IV injectafer vs oral iron (to avoid patient selection bias) in GIST patients with IDA planning to start or have recently started systemic therapy to evaluate efficacy and safety with IV injectafer.

3.0 Background Drug Information

3.1 Ferric Carboxymaltose (Injectafer)

Injectafer® (ferric carboxymaltose injection) is a colloidal iron (III) hydroxide in complex with carboxymaltose, a carbohydrate polymer that releases iron [20].

A. Physical Description of Study Drug

Injectafer® is a dark brown, non-transparent amorphous powder that is readily soluble in water. The active pharmaceutical ingredient of Injectafer® contains about 28% weight to weight (w/w) of iron, equivalent to about 53% w/w iron (III) hydroxide, about 37% w/w of ligand, \leq 56% w/w of sodium chloride and \leq 10% w/w of water [20].

B. Formulation Packaging, Labeling and Storage

Ferric carboxymaltose, an iron replacement product, is an iron carbohydrate complex with the chemical name of polynuclear iron (III) hydroxide 4(R)-(poly-(1 \rightarrow 4)-O- α -D-glucopyranosyl)-oxy-2(R),3(S),5(R),6-tetrahydroxy-hexanoate. It has a relative molecular weight of approximately 150,000 Da corresponding to the following empirical formula: $[FeO_x(OH)_y(H_2O)_z]^n \cdot \{(C_6H_{10}O_5)_m \cdot (C_6H_{12}O_7)\}_k$, where $n \approx 10^3$, $m \approx 8$, $l \approx 11$, and $k \approx 4$ (l represents the mean branching degree of the ligand)[20].

Injectafer will be supplied as 15 mL vials, containing 750 mg of iron as 5% w/v iron solution in water for injection.

The dosage of Injectafer® is expressed in mg of elemental iron. Each mL of Injectafer® contains 50 mg of elemental iron. Injectafer® is intended for intravenous (IV) administration, either as a slow IV push or by IV infusion. When administered as a slow IV push, Injectafer® can be injected without dilution at a rate of 100 mg/minute. When

administered as an infusion, up to 750 mg of Injectafer® is diluted in no more than 250 mg of sterile 0.9% weight to volume (w/v) sodium chloride, such that the concentration of the infusion is not less than 2 mg of iron/mL and administered over 15 minutes. No other IV dilution solutions should be used and no other therapeutic agent should be added, as there is a potential for interaction.

All IV study drugs will be supplied by Luitpold Pharmaceuticals, Inc. They should be kept in a secure place at the investigational site, and stored at room temperature (see: USP). The study medication should not be frozen. **Vials may not be used for more than 1 dose or for more than 1 subject.**

C. Drug Accountability

Ferric Carboxymaltose (Injectafer®) will be provided by Luitpold Pharmaceuticals, Inc. from the commercial drug supply according to Good Manufacturing Practices (GMP).

It is the responsibility of the clinical investigator or trained designee to ensure that all study drug received at the site is inventoried and accounted for throughout the study by the designated personnel and is recorded in the inventory log kept with the pharmacy study documentation. The drug accountability will be verified by a trained designee upon completion of the study. Study drug will be stored in a secured area with restricted access to the dosing preparers only.

The clinical investigator or trained designee must store all study drugs pending reconciliation. The investigator agrees that study drug(s) will be dispensed by the investigator or sub-investigator(s) named on the Investigator Agreement or their qualified designees. The investigator, sub-investigators, or qualified designees also agree that the study drug(s) will be dispensed only to study subjects who have provided written informed consent and have met all entry criteria and in accordance with the instructions provided in the pharmacy manual.

After study drug reconciliation, the clinical site may destroy used/unused study drug product locally in accordance with all applicable institutional standard operating procedures, local and federal laws. Documentation of such destruction must be recorded and provided Luitpold Pharmaceuticals, Inc.

D. Contraindications

Hypersensitivity to Injectafer® or any of its inactive components.

3.2 Oral Iron Supplement

Oral iron supplement like Ferrous sulphate, Ferrosequels will be used from the commercial source.

3.3 Other Drugs

TKIs like Imatinib/Gleevec, sunitinib are all commercially available drugs.

4.0 Patient Eligibility

Inclusion Criteria

- 1) GIST patients with IDA planned to start or receiving systemic therapy with TKIs
- 2) Evidence of iron deficiency anemia including, Hgb \leq 11 g/dL, but \geq 8 g/dL; and transferrin saturation (TSAT) $<$ 20%.
- 3) No H/O allergic reaction to iron therapy.
- 4) No clinical signs active of bleeding.
- 5) Adequate hematologic (ANC $>$ 1500/mm³, platelet count $>$ 100,000/mm³), renal (serum creatinine $<$ 1.5mg/dL), hepatic (serum bilirubin count $<$ 1.5 x normal and SGOT or SGPT $<$ 3 x normal) functions.
- 6) Patients must have Eastern Cooperative Oncology Group (ECOG) performance status of 0 – 2.
- 7) Signed informed consent to the study.
- 8) Male and Females of child bearing potential must use acceptable methods of birth control which include oral contraceptives, spermicide with either a condom, diaphragm or cervical cap, use of an intrauterine device (IUD) or abstinence.
- 9) Patients are required to read and understand English to comply with protocol requirements.
- 10) Age \geq 18 years old.
- 11) Life expectancy of at least 6 months.

Exclusion Criteria

- 1) Pregnant or lactating women.
- 2) Patients with any co-morbid condition which renders patients at high risk of treatment complication.
- 3) Patient has uncontrolled angina, congestive heart failure (New York Heart Association > class II or known ejection fraction $<$ 40%), uncontrolled cardiac arrhythmia or hypertension, or acute myocardial infarction within 3 months.

- 4) Patient has an active seizure disorder. (Patients with a previous history of seizure disorders will be eligible for the study, if they have had no evidence of seizure activity, and they have been free of antiseizure medication for the previous 5 years).
- 5) Psychological, social, familial, or geographical reasons that would prevent scheduled visits and follow-up.
- 6) Prior surgery or radiotherapy (RT) within 2 weeks of study entry.
- 7) Known hypersensitivity reaction to any component of ferric carboxymaltose.
- 8) Any anemia treatment within 4 weeks before inclusion (oral iron, IV iron, or erythropoiesis-stimulating agents), or transfusion of PRBCs in 2 weeks.
- 9) Hemochromatosis or other iron storage disorders.
- 10) Known positive hepatitis with evidence of active disease.
- 11) Patients with overt bleeding.
- 12) Ferritin \geq 800 ng/mL.

5.0 Treatment Plan

5.1 Study Drug Treatment

This is an open label, randomized, phase II trial. Approximately 50 evaluable subjects will be randomly assigned to arm A and arm B (1:1).

Prior to randomization, all patients will be stratified into < 10g/dL vs. \geq 10g/dL.

Treatment Plan:

Fifty patients with GIST will be randomized 1:1 into two treatment arms; total 25 patients in each of the two arms:

Arm A/ investigational arm: all subjects (n=25) will receive 2 doses of Injectafer® at 15 mg/kg for a maximum single dose of 750 mg, given 7 days apart for a total of up to 1500 mg. The first IV infusion will be given prior to starting systemic therapy. The dose will be repeated 1 week later. It will be diluted in no more than 250 mL of normal saline and infused over 15 minutes.

Arm B/control arm: all patients (n=25) will receive oral iron (dose equivalent of 150-200 mg of elemental iron/day) supplement daily (such as Ferrosequels, BID, or ferrous sulphate, TID) for 3 months. Different iron preparation can be used based on patient's tolerance/preference.

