11.0 Statistical Consideration and Sample Size

Statistical Considerations and Analysis

This study will assess the efficacy of IV Injectafer in improving HGB level in GIST patients planned to receive or receiving systemic therapy and presenting with anemia.

Design and Sample Size/Power

This is a randomized, open label, 2-arm trial of 2-dose IV Injectafer in patients with GIST planned to receive or receiving systemic therapy and presenting with anemia. Arm A patients will receive 2 doses of IV Injectafer over 15 min infusion (prior to start systemic therapy and another same dose 1 week later). Arm B patients will receive oral iron supplement (such as Ferrosequels BID, or ferrous sulphate TID) for 3 months. The primary objective is to evaluate the efficacy of IV Injectafer in patients with GIST planned to receive or receiving systemic therapy and presenting with anemia as compared to the effect of oral iron supplement.

A patient will be considered as to have a complete response (CR) if his/her HGB level increase ≥ 2 g/dL from baseline to any time during 3 months following initiation of the study drug, and/or transfusion free. The primary endpoint is CR rate in 3 months. A total of 50 patients, 25 in each arm, will provide the study 93% power to detect the differences of response between the two arms using a Chi-square test with a 0.05 two-sided significance level when the respective CR rates are 75% (6/8) and 28.6% (8/28) in Arm A, and B (according to our clinical experience). All patients who are randomized will be evaluable for response in the intent-to-treat analysis. nQuery 7.0 was used for the sample size or power calculation.

Analysis Plans

Patients' demographic and clinical characteristics at baseline will be summarized using descriptive statistics such as mean, standard deviation, median, interquartile range (IQR), frequency where appropriate. We will apply Student t-test/Wilcoxon test and Kruskal-Wallis test/ANOVA to compare continuous variables between different patient group, and the chi-square test or the Fisher's exact test to assess the association between two categorical variables [25].

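### Arm A's first infusion must precede systemic therapy, yet patients already on a TKI are eligible and Arm B has no matching timing rule

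*Combined protocol and SAP*

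**What the plan says.** **Who may enter.** Inclusion criterion 1 in Section 4.0 reads "GIST patients with IDA planned to start or receiving systemic therapy with TKIs", with no limit on how long a patient may already have been treated. The objectives (Section 1.0) and the design text (Section 11.0) describe the same two-part population. The rationale (Section 2.5) is narrower, describing patients "planning to start or have recently started systemic therapy".

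**Arm A.** Section 5.1 opens with "Arm A/ investigational arm: all subjects (n=25) will receive 2 doses of Injectafer" and continues "The first IV infusion will be given prior to starting systemic therapy". Section 11.0 gives the schedule again as "prior to start systemic therapy and another same dose 1 week later".

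**Arm B.** Section 5.1 says "all patients (n=25) will receive oral iron (dose equivalent of 150-200 mg of elemental iron/day) supplement daily" for 3 months. Section 11.0 says "Arm B patients will receive oral iron supplement (such as Ferrosequels BID, or ferrous sulphate TID) for 3 months". Neither relates the start of oral iron to the start of systemic therapy. Section 5.2 calls the background treatment standard TKI-based therapy and sets no start date in either arm.

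**Endpoint and analysis.** The primary endpoint is the complete response (CR) rate in 3 months. CR rests on a hemoglobin rise of at least 2 g/dL, counted from the start of study drug; the definition also has a transfusion element, which is not at issue here. Randomization is stratified on baseline hemoglobin only. The logistic model in Section 11.0 names treatment group and gender as examples of covariates and does not mention TKI status.

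**The concern.** Two things go wrong if the text is followed as written.

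First, some eligible patients cannot be treated according to protocol. Someone already on a TKI cannot receive an infusion before that therapy starts. This arises in Arm A only, so departures from the written schedule are built into one arm and sites must decide for themselves how to handle them.

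Second, the timing rule belongs to one arm. For patients yet to start a TKI, iron comes first in Arm A by rule, while in Arm B the order is left to the site. The protocol gives its own reason why this may matter: Section 2.2 says that TKIs may reduce red-cell production, and Section 2.5 says "anemia often worsens during therapy with TKIs like Gleevec". When a TKI starts relative to the baseline hemoglobin and the 3-month window could therefore affect whether a patient reaches CR. Randomization balances TKI use before entry in expectation. It does not protect against a difference that an arm-specific instruction creates afterwards, and because the trial is open label the site knows which patients the instruction binds.

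**Working it through.** **1. The plan's own figure.** Inputs from Section 11.0: 25 patients per arm, CR rates 0.75 and 0.286, chi-square test, two-sided 5% level.

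- Difference = 0.75 − 0.286 = 0.464; pooled rate = (0.75 + 0.286)/2 = 0.518.
- Standard error under no difference = √(2 × 0.518 × 0.482 / 25) = 0.1413.
- Standard error under the alternative = √[(0.75 × 0.25 + 0.286 × 0.714) / 25] = 0.1252.
- z = (0.464 − 1.96 × 0.1413) / 0.1252 = 1.49, so power = 0.932.

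The stated 93% is reproduced. This point does not dispute it.

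**2. Eligibility set against the timing text.**

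| TKI status at randomization | Arm A | Arm B |
|---|---|---|
| Not yet started | Iron must come first; can be met | Order not stated |
| Already receiving | Iron must precede a start that is already past; cannot be met | No rule, so nothing to breach |

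The contradiction lies in one cell (Arm A, already receiving). The asymmetry lies in the top row. The timing appears in both the treatment plan and the statistical section, so it is not a stray phrase.

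**3. How many patients could be affected.** The documents do not give the share already on a TKI. If it is s, about 25 × s Arm A patients cannot comply. For an assumed 25% this is 0.25 × 25 = 6.25, about 6; for an assumed 75% it is 0.75 × 25 = 18.75, about 19. The number in Arm B is 0. These are counts of departures from the written schedule and do not measure bias.

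**4. Can the bias be sized?** That would need the share of patients in whom the order really differs by arm, the length of the gap, and the effect of TKI exposure on CR. The documents give none of these.

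The direction is open too. A later TKI start could mean less exposure within the window and so more rises. But a TKI begun before baseline may already have lowered the starting hemoglobin, which leaves more room for a rise. Arm B patients might also simply receive iron first, in which case timing would not differ at all.

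**The case against.** The strongest reply is that this is a missing qualifier. The phrase about all subjects governs the sentence on two doses. The timing sentence speaks of starting therapy, which can describe only patients who have not started. Section 11.0 puts the two-part population and the timing in the same paragraph, so the authors may have seen no conflict. That reading is plausible, but the text does not state it. It would remove the impossibility and leave the Arm A-only rule in place. It is also fair that the phrase in Section 2.5 is background and that Section 4.0 is the operative criterion.

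Other parts of the reply stand in full, and they rule out stronger readings that a reader might infer:

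- *That Arm A patients will be excluded after randomization.* Sections 9.1 and 11.0 keep every randomized patient in the efficacy analysis. The toxicity analysis keeps anyone who has had a dose, whatever their eligibility. Section 10.0 does not name a timing departure as a reason to stop.
- *That TKI timing does differ by arm.* The documents show a rule in one arm and silence in the other. Nothing says that Arm B patients start their TKI before oral iron.
- *That the arm difference shifts by 5 to 10 points.* One could assume that TKI exposure costs 10 to 20 points of CR and that order differs in half the patients: 0.5 × 10 to 20 = 5 to 10 points. This treats order as if it were exposure. No minimum gap is set, so a compliant Arm A patient may start a TKI soon after the infusion and be exposed for nearly the whole window. If the effect is scaled to unexposed time, with an assumed gap of 1 to 7 days in a 90-day window, the result runs from 0.5 × 10 × 1/90 = 0.06 to 0.5 × 20 × 7/90 = 0.8 points. Both ranges rest wholly on assumptions.
- *That chance imbalance in TKI status adds to the problem.* With half the patients on a TKI, the difference in counts between arms has standard deviation √(2 × 25 × 0.25) = 3.5. A gap of 5 or more patients (20 points) then has probability about 0.20. The arithmetic is right, but this is ordinary sampling variation. It would be the same without the timing sentence, and the test's 5% error rate already allows for it.

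**Conclusion.** The plan is inconsistent as written. Patients already on a TKI are eligible, but if randomized to Arm A they cannot meet the stated timing of the first infusion. The rule is also given for one arm only, so the order of iron and TKI is fixed in Arm A and open in Arm B for patients yet to start.

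On the protocol's own account of TKIs and anemia, that makes the rule an avoidable possible source of bias in the primary comparison. The documents do not allow its size or direction to be computed. They do not show that bias will occur, or that the planned contrast of 46.4 points is at risk. The conclusion rests on a literal reading of Sections 4.0, 5.1 and 11.0 and on the protocol's statements that TKIs can worsen anemia. It needs no assumption about the share of patients on a TKI, beyond some being enrolled.

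**What to change.** 1. Reconcile Sections 2.5, 4.0, 5.1 and 11.0, so that one statement on the timing of study drug relative to TKI can be met by every eligible patient and applies equally to both arms. The choice of rule belongs to the sponsor and the investigator.
2. Record TKI status at randomization (receiving or planned) and the TKI start date for every patient.
3. In the logistic model of Section 11.0, name TKI status and the baseline-hemoglobin stratum as covariates alongside treatment, as a supportive adjusted analysis. The chi-square test stays primary. TKI status at entry is a baseline variable, so this can add precision and deal with chance imbalance, but it cannot correct a timing difference that arises after randomization. Only step 1 prevents that.

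The cost is a short amendment, one baseline status item and one date on the case report form, and slightly more analysis work. No extra patients or procedures are needed.
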